2.4. Primary Efficacy Endpoint Rationale

The primary objective of the study is to determine the effectiveness of the therapy in improving TBUT in eyes with DED due to MGD. This objective was chosen because a reduced TBUT is one of the most common signs of DED due to MGD. TBUT is considered abnormal when shorter than 10 seconds.

In this study we wish to compare the Tixel device to a marketed device, the LipiFlow system. In the comparative study of iLux vs LipiFlow the chosen NI margin was 2.5 seconds⁴. Since a criterion for clinically relevant improvement in TBUT has not been defined, clinical relevance was based on the labeling of the DET test strip which defines the difference between dry and normal tear stability as 5 seconds. Thus, a change of 2.5 seconds was defined as a clinically relevant change since it represents 50% of that defined in the DET strip labeling.

⁴ Tauber J, Owen J, Bloomenstein M, Hovanesian J, Bullimore MA. Comparison of the iLUX and the LipiFlow for the Treatment of Meibomian Gland Dysfunction and Symptoms: A Randomized Clinical Trial. Clin Ophthalmol. 2020 Feb 12;14:405-418.

3. STATISTICAL CONSIDERATIONS

3.1.General Considerations

Descriptive statistics will be used to summarize continuous variables (number of eyes/patients [N], mean, standard deviation (SD) or standard error of the mean, median, maximum, and minimum) and categorical variables (frequency and percentage) at each assessment timepoint. Statistical comparisons within each group will be performed using appropriate statistical methods or models, and the results such as 95% confidence intervals and p values will be reported. All summary tables will be supported with individual patient and eye data listings. Baseline is defined as the last non-missing observation prior to initiation of study intervention. Analyses will be carried out using SAS software or equivalent statistical software.

Novoxel

Further details will be described in the statistical analysis plan, which will be finalized prior to the study database lock.

3.2. Analysis Populations

- Intent-to-Treat Population: The intent-to-treat (ITT) population includes all randomized patients. Patients will be analyzed as randomized.
- Per Protocol Population: The per protocol (PP) population includes all patients who performed the 4 weeks follow-up visit, completed all the treatments as randomized, and have no major protocol deviations. Patients will be analyzed as treated. The primary analysis population will be the per-protocol (PP) population.
- Safety Population: The safety population will include all treated patients. The safety population will be analyzed for all safety assessments. Patients will be analyzed as treated. A summary table of number (%) of patients in each analysis population/set will be provided.

3.3.Demographic and Baseline Characteristics

Descriptive statistics or frequency tabulation will be provided for demographic and baseline characteristics, such as age, gender, race, and ethnicity.

3.4.Effectiveness Analyses

3.4.1. Primary effectiveness endpoint

 The primary endpoint of change from baseline in the TBUT as rated by a masked rater at 4 weeks will be analyzed for non-inferiority using a margin of 2.5 seconds. The primary non-inferiority hypothesis set will be: Ho: $\mu_{\text{Tixel}} - \mu_{\text{Lipiflow}} + \delta \le 0$

HA: $\mu_{\text{Tixel}} - \mu_{\text{Lipiflow}} + \delta > 0$

where μ_{Tixel} and $\mu_{Lipiflow}$ are the mean TBUT changes from baseline at 4 weeks for Tixel and Lipiflow, respectively and $\delta=2.5$.

NoVoxel

A change in TBUT of at least 2.5 seconds in each group will be considered clinically significant.

The difference between Tixel and Lipiflow in changes from baseline in TBUT as rated by a masked rater at 4 weeks will be assessed using a linear mixed-effects model with a random effect for subjects and fixed effect for treatment and baseline score as covariate. The random-effect adjusts the "within-subject correlation" between eyes. Least square means will be estimated by treatment arm from the model. The confidence interval for the estimates will be one-sided and a test value of 2.5 will be used to test non-inferiority.

3.4.2. Secondary effectiveness endpoints

- 1- OSDI
 - The change from baseline at 4 weeks and 12-weeks in the Ocular Surface Disease Index (OSDI) will be calculated along with 95% confidence interval. The Paired T-test or Signed rank test for two means (paired observations) (as is appropriate) will be applied for testing the statistical significance of the changes within each study group.
 - The two-sample T-test or Non-parametric Wilcoxon-Mann-Whitney Rank sum test for independent samples (as is appropriate) will be applied for testing the statistical significance of the difference in change from baseline in OSDI at week 4 between the study groups
- 2- MGS
 - The difference between Tixel and Lipiflow in changes from baseline in MGS as rated by a masked rater at 4 weeks and 12 weeks will be assessed using a linear mixed-effects model with a random effect for subjects and fixed effect for treatment and baseline score as covariate. The random-effect adjusts the "within-subject correlation" between eyes. Least square means will be estimated by treatment arm from the model.
- 3- TBUT

18-Jan-2023

Clinical Protocol Number: CLN 0858 Rev. 007

In 12 weeks, the follow-up visit will be analyzed in the same way as the 4-weeks follow-up visit.

3.4.3. Exploratory Analysis:

_

- For each follow-up (4 weeks and 12 weeks), if non-inferiority is achieved, the TBUT score change from baseline as rated by a masked rater at the relevant follow will be analyzed for superiority. The hypothesis set will be:
- Ho: $\mu_{Tixel} \mu_{Lipiflow} \le 0$
- HA: $\mu_{\text{Tixel}} \mu_{\text{Lipiflow}} > 0$

3.5.Handling of Missing data

Every effort will be made to complete follow-up for all patients and avoid missing data, in particular regarding the primary endpoint variable. However, in the event data is missing, multiple imputation will be used. Further details will be provided in the statistical analysis plan.

3.6.Interim Analysis

No interim analyses are planned for this study.

3.7.Sample Size Justification

55 patients will be enrolled in each treatment group.

Sample size rationale:

The sample size calculation is based on the primary efficacy endpoint. Specifically, the sample size calculation was based on the non-inferiority with a 2.5 second margin of the change from baseline in TBUT score as assessed by a masked rater at 4 weeks follow-up for Tixel versus LipiFlow. The expected standard deviation of the difference in change is 4.5 seconds.

The calculation assumes the worst-case scenario that the TBUT of both subjects eyes subjects is completely correlated (r=1).

Sample size justification:

When the sample size in each group is 44, a two group one-sided 0.05 significance level t-test will have 80% power to reject the null hypothesis that the test and standard are not non-inferior (the difference in means, μ_T - μ_L , is 2.5 seconds or farther from zero in the same direction) in favor of the alternative hypothesis that the means of the two groups are non-inferior, assuming that the expected difference in means is 0 and the common standard deviation is 4.5 s.

Assuming a 20% drop-out rate, 55 patients will be enrolled in each group ensuring a sample size of 44 patients per group.

Novoxel

[4 -Dixon et al, 1983; 5 O'Brien et al, 1993]

3.8.Poolability Analysis

Patient demographic characteristics and background variables shall be summarized.

The primary endpoint analysis will be conducted for each investigational site. The justification for pooling all the data to estimate a common effect across study sites requires the homogeneity of response across study sites. An analysis of variance (ANOVA) of the differences will be generated to test whether the investigational sites differ with respect to primary study endpoint (only the site will be included in this analysis model). The test of inhomogeneity of response will be based on a two-sided significance test at the 0.15 level of significance. If the sites differ by this test, then a second analysis will be done including study site and all baseline characteristics that have P<0.10 in the analysis of baseline characteristics by site to understand if the imbalance in the primary endpoint between sites is related to an imbalance in baseline characteristics.

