1. STUDY SYNOPSIS

Study Name	A Randomized, Masked (Evaluator), Controlled, Prospective Study
	evaluating the Effectiveness and Safety of the Tixel [®] Medical Device,
	Versus LipiFlow [®] in the Treatment of Meibomian Gland Dysfunction
Study Device	Tixel C
Stage of	Pivotal study to support an indication for use of treatment of Meibomian
Development	Gland Dysfunction
General Design	The study includes 2 stages: stage 1 is the main pivotal protocol, and stage 2
	is an extension study for a sub-group population which completed the main
	protocol, was treated with the Tixel device and meets specific criteria of
	clinical benefit (specified in the description of stage 2 below).
	Stage 1- the main protocol
Design	• Randomized, open-label study comparing the Tixel device to
	LipiFlow System.
	• Up to 110 patients (220 eyes) to be randomized in up to 6 clinical sites
	in the United States.
	• Evaluators will be masked as to the randomization assignments.
	• Both eyes will receive the same randomized assignment and both eyes
	of each patient will be evaluated at all time points.
	• Data from both eyes will be using in the statistical analysis.
	The random-effects model adjusts the standard error (SE) and the confidence
	interval (CI) for within-person correlation between eyes.
Objective	Evaluate the safety and effectiveness of the Tixel C device in adults with
	Meibomian Gland Dysfunction (MGD).
Primary	Change from baseline to the 4-weeks follow-up exam in Tear Break Up Time
Effectiveness	(TBUT).
Endpoint	
Secondary	• Change from baseline in patient symptoms using Ocular Surface Disease
Effectiveness	Index (OSDI) at 4-weeks and 12-weeks follow-up exam.
Endpoints	

	• Change from baseline to 4-weeks and 12-weeks follow-up exam in
	Melbomian Gland Score (MGS).
	• Change from baseline to 12-weeks follow-up exam in Tear Break Up Time
	(TBUT).
Key Safety	Comparison of the incidence of Ocular Adverse Events for the two treatment
Endpoint	arms.
Secondary Safety	• The evaluation of discomfort and pain during treatment.
Endpoints	• Changes from baseline following treatment for the test and control devices
	for the following assessments:
	° Ocular Surface Staining.
	° Intraocular Pressure.
	° Best corrected distance Visual acuity.
Population	Adult patients with symptoms of evaporative dry eye/MGD who do not
	respond adequately to conservative treatment options such as ocular
	lubricants.

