Sample size	Up to 110 patients (220 eyes), 55 patients per device to be enrolled at up to 6
	study sites in the US, will serve as sample size to investigate whether the Tixel
	C device is non-inferior to the LipiFlow system in terms of change in TBUT
	from baseline to 4 weeks following the last treatment.
	Sample size rationale:
	The sample size calculation is based on the primary effectiveness endpoint.
	Specifically, the sample size calculation was based on the non-inferiority with
	a 2.5 seconds' margin of the change from baseline in TBUT score as assessed
	by a masked rater at 4 weeks follow-up for Tixel versus LipiFlow. The
	expected standard deviation of the difference in change is 4.5 seconds.
	The calculation assumes the worst case scenario that the TBUT of both eyes
	of subjects are completely correlated (r=1).
	Sample size justification:
	When the sample size in each group is 44, a two group one-sided 0.05
	significance level t-test will have 80% power to reject the null hypothesis that
	the test and standard are not non-inferior (the difference in means, μ_T - μ_L , is
	2.5 s or farther from zero in the same direction) in favor of the alternative

	hypothesis that the means of the two groups are non-inferior, assuming that
	the expected difference in means is 0 and the common standard deviation is
	4.5 s.
	Assuming a 20% drop-out rate (a relatively high rate is currently assumed due
	to Covid-19 uncertainty), 55 patients will be enrolled in each group ensuring
	a sample size of 44 patients per group.
Inclusion Criteria	1. Age 22 years and older of any gender or race.
	2. Provision of written informed consent prior to study participation.
	3. Willingness and ability to return for all study visits.
	4. Reports dry eye symptoms for three months prior to the study.
	5. Ocular Surface Disease Index (OSDI) score between 23-79.
	6. Tear break-up time (TBUT) ≤ 10 seconds in both eyes.
	7. Agreement/ability to abstain from dry eye/MGD medications for the
	time between the treatment visit/s and the final study visit. Ocular
	lubricants are allowed if no changes are made during the study.
	8. Reports having to use artificial tears or lubricants regulatory over the
	past month to relieve dry eye symptoms.
	9. Meibomian gland obstruction in both eyes based on a total Meibomian
	Gland Secretion Score ≤ 12 in each eye.
	10. At least 15 glands in each lower eyelid should be expressible, with a
	sterile cotton swab, at the slit lamp.

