	30. Use of Botulinum-Toxin in the last 6 months prior to the treatment in
	the treatment area.
	31. Co-existing condition, either ocular or non-ocular that, in the
	judgement of the investigator could affect the safety or effectiveness
	of treatment or the compliance of the subject to the protocol.
Schedule of	Screening: (Must be done within 7 days prior to initial treatment (Day 0), but
Screening and	can be also done on the same day as baseline testing and initial treatment)
Baseline	Informed Consent
Evaluations	Demographics/medical/ocular history
For Tixel and	Concomitant systemic and ophthalmic medications
LipiFlow Groups	• Patient's report of the daily usage (frequency and dose) of eye
	lubricants
	• Determination of Fitzpatrick skin type
Pre-	Pre-Treatment/Baseline: (Must be done within 5 days prior to initial treatment
Treatment/Baseline	but can be also done on the same day. All assessments must be done before
	randomization and performing either treatment)- the tests must be done in this
	order and by a masked investigator.
	• OSDI (administer first, self-assessed)
	Refraction
	Best Corrected distance visual acuity
	• Keratometry
	• Slit Lamp for Anterior Segment Health

	• Eyelid Margin Assessment (including development of entropion or
	ectropion, floppy eyelids, lash integrity assessment)
	• TBUT
	Corneal Fluorescein Staining Slit Lamp Evaluation
	Conjunctival staining Lissamine green
	Meibomian Gland Assessment and Scoring
	• Meibomian Gland expressibility test- At least 15 glands in each lower
	eyelid should be expressible, with a sterile cotton swab, at the slit
	lamp.
	Intraocular pressure
Randomization	Randomization: (Performed after determining that the patient is eligible for
	the study)
	Patients will be randomized to the Tixel or control LipiFlow group in a 1:1
	ratio. Randomization will take place prior to patient treatment. The
	randomization allocation will be given to the patient directly from the EDC
	system.
	Schedule of Treatments – Tixel Crown
	Schedule of Treatments – Tixel Group
Treatment 1	Schedule of Treatments – Tixel Group
Treatment 1 Tixel Group	Schedule of Treatments – Tixel Group Image: Treatment 1 (Day 0): Testing must be done in this order:
Treatment 1 Tixel Group	Schedule of Treatments – Tixel Group Treatment 1 (Day 0): Testing must be done in this order: • Patient's report of the daily usage (frequency and dose) of eye

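### At week 12 the only OSDI test is a within-arm one, and a significant within-arm OSDI change cannot be attributed to the device

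*Combined protocol and SAP*

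**What the plan says.** Section 3.4.2 (item 1, OSDI) gives two analyses. The first covers weeks 4 and 12: change from baseline with a 95% confidence interval, and a paired t or signed-rank test for "testing the statistical significance of the changes within each study group". The second is a two-sample t or rank-sum test for "testing the statistical significance of the difference in change from baseline in OSDI at week 4 between the study groups". It has no week-12 counterpart, no baseline covariate and no margin. Section 3.1 adds, for all endpoints, that "Statistical comparisons within each group will be performed using appropriate statistical methods or models", with intervals and p values.

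Four other provisions matter:

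- **Entry.** Inclusion criterion 5 in the Synopsis requires "Ocular Surface Disease Index (OSDI) score between 23-79".
- **Baseline.** Section 3.1: "Baseline is defined as the last non-missing observation prior to initiation of study intervention". In the Synopsis schedule, "OSDI (administer first, self-assessed") is in the Pre-Treatment/Baseline list and not in the Screening list. On that schedule one score both qualifies the patient and serves as baseline.
- **Control.** "Patients will be randomized to the Tixel or control LipiFlow group in a 1:1" ratio. Both arms receive an active device.
- **Masking.** The Synopsis describes a "Randomized, open-label study comparing the Tixel device to" LipiFlow. Evaluators are masked; patients are not.

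**The concern.** A paired test within one arm asks only whether the mean moved. Here it can move for three reasons unrelated to the device:

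- regression to the mean, because patients were selected on the same measurement that serves as baseline;
- the response of unmasked patients rating their own symptoms;
- the natural course of the condition.

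Randomisation protects a between-arm contrast from these so far as they act equally in both arms. It does nothing for a within-arm test.

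The Introduction says the study is meant to show that Tixel is safe and effective. A small within-arm p value for symptoms could easily be quoted as support. At week 12 the plan offers no randomised OSDI comparison to set beside it. MGS and TBUT do get a baseline-adjusted between-arm model at both visits, so OSDI, the one self-rated endpoint of the three, has the weakest comparison.

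**Working it through.** **Plan's own figures.** The plan states no power or error rate for OSDI, so there is none to reproduce. The relevant input is the evaluable number per arm (section 3.7): 55 × (1 − 0.20) = 44.

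**Assumed inputs.** The documents give no OSDI mean, SD or reliability. Assumed for the screened population: mean m from 25 to 60, SD s of 15-20, test-retest reliability r of 0.60-0.85. The true score does not change.

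**Formulas.** Let a = (23 − m)/s, b = (79 − m)/s and P = Φ(b) − Φ(a).

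- λ = [φ(a) − φ(b)]/P
- Mean spurious change = −(1 − r)·s·λ
- V = 1 + [aφ(a) − bφ(b)]/P − λ²
- SD of change = √[(1 − r)²s²V + s²(1 − r²)]
- Non-centrality = mean change / SD × √44, referred to noncentral t with 43 df, critical value 2.017

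**Worked case: m = 35, s = 20, r = 0.70.** a = −0.6, b = 2.2, P = 0.712.

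- λ = (0.3332 − 0.0355)/0.712 = 0.418
- Mean change = −0.30 × 20 × 0.418 = −2.5 points
- V = 0.4345; SD = √(0.09 × 400 × 0.4345 + 400 × 0.51) = 14.8
- Non-centrality = −2.51/14.82 × 6.633 = −1.12
- Significant improvement in 19.4% of arms (nominal 2.5%); any rejection in 19.6% (nominal 5%)
- At least one of the two arms significantly improved: 1 − (1 − 0.194)² = 35% of trials

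**Ends of the range for m = 25-40.**

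- m = 25, s = 20, r = 0.60: λ = 0.721, mean change −5.8, SD 16.7, non-centrality −2.29, rejection 61%.
- m = 40, s = 15, r = 0.85: λ = 0.227, mean change −0.5, SD 8.1, non-centrality −0.42, rejection 7%.

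**Over the whole range** (n = 44, two-sided 5% paired t-test, no true change):

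| Screened mean | Rejection rate | Direction |
|---|---|---|
| 25 | about 26-61% | improvement |
| 30 | about 16-41% | improvement |
| 35 | about 10-25% | improvement |
| 40 | about 7-14% | improvement |
| 45 | about 6-7% | mostly improvement |
| 51 | 5% (nominal) | none |
| 60 | about 6-11% | mostly worsening |

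At m = 51, the centre of the window ((23 + 79)/2), a = −b, so λ = 0 for any s and r. Simulation with scores held to 0-100 (assumed scale) agrees with the formula to within about one percentage point in the cases compared.

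**Second route, independent of the entry window.** Suppose a non-device shift of 4 points and an SD of change of 12-20 (assumed). The non-centrality is 4/20 × √44 = 1.33 to 4/12 × √44 = 2.21, giving significance in 25-58% of arms. A shift of 8 points gives 74-99%.

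**Between-arm test on the same null data.** Five simulated scenarios with regression to the mean gave a two-sided false-positive rate of 4.8-5.1%.

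**The case against.** The strongest reply is that the paired test is valid for what section 3.4.2 says it tests. The plan does not call it a test of device effect and attaches no success criterion to it. Effectiveness rests on the TBUT non-inferiority comparison in section 3.4.1, which is masked, adjusted for baseline and between arms. A between-arm OSDI test already exists at week 4. All of this is true, and it makes the point minor. It does not supply a randomised OSDI comparison at week 12.

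The second reply concerns direction and size, and it stands. A reader might infer that scores selected this way must fall, or that the error rate is well above 5%. The documents support neither. Criterion 5 cuts at both ends, and the upper limit pulls the other way. Candidates must report three months of symptoms and regular lubricant use, so a low screened mean cannot be presumed. At a mean of 25, about 45% of those screened would fall outside the window, nearly all below 23; the 61% figure belongs to that corner.

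A reader might also infer that every within-group p value promised in section 3.1 should go. The argument here covers OSDI only.

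**Conclusion.** The point holds as a limited one about a secondary endpoint. The documents themselves establish that the within-arm test is the only OSDI test at week 12, and that a significant within-arm change, at either visit, cannot be attributed to the device.

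How often such a result would arise with no device effect is not known. From regression to the mean alone it is about 7-61% at n = 44, conditional on a screened mean of 25-40, SD 15-20 and reliability 0.60-0.85. It is nominal near a mean of 51, and above that the bias would count against the device. Open-label response and natural course do not depend on the screened mean, but their size is equally unstated.

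It would be wrong to infer that the primary conclusion is at risk: the TBUT comparison is between arms and adjusted for baseline.

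**What to change.** In section 3.4.2:

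1. Replace the within-arm OSDI significance tests with within-arm mean change and 95% confidence interval at each visit, labelled descriptive and not evidence of a device effect. The label is needed because an interval that excludes zero carries the same message as the paired t-test. Say that the general provision for within-group p values in section 3.1 does not apply to OSDI.
2. Base OSDI inference on the between-arm difference at week 4 and week 12, adjusted for baseline OSDI as already planned for MGS and TBUT. OSDI is one score per patient, so a linear model with treatment and baseline is enough at each visit. If non-inferiority on OSDI is intended, state a margin.
3. State that a non-significant difference between two active devices does not by itself show that either is effective.
4. Note when interpreting the comparison that follow-up counts from the last treatment. Tixel has two further sessions at two-week intervals, so its visits fall about 2 × 2 = 4 weeks later after baseline than LipiFlow's. Time-related change need not cancel fully.

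The cost is wording only, with no new visits or data. The downside is that within-arm OSDI p values can no longer be quoted.

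### OSDI at 12 weeks is a listed secondary endpoint with no comparison between devices, and the week-4 comparison leaves out baseline OSDI

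*Combined protocol and SAP*

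**What the plan says.** The synopsis, under Secondary Effectiveness Endpoints, gives change from baseline in symptoms by the Ocular Surface Disease "Index (OSDI) at 4-weeks and 12-weeks follow-up exam".

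Section 3.4.2, item 1 (OSDI), plans three things:

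- The change from baseline at 4 and 12 weeks, with a 95% confidence interval.
- A paired t-test or signed rank test, "applied for testing the statistical significance of the changes within each study group".
- A two-sample t-test or Wilcoxon-Mann-Whitney test for "testing the statistical significance of the difference in change from baseline in OSDI at week 4 between the study groups". No covariate is named.

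Item 2 (MGS) compares the arms at 4 and 12 weeks in a mixed model with "random effect for subjects and fixed effect for treatment and baseline score as covariate". The primary TBUT model in section 3.4.1 has the same structure. Item 3 (TBUT) consists of one sentence: "In 12 weeks, the follow-up visit will be analyzed in the same way as the 4-weeks follow-up visit".

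**The concern.** Section 2 states the aim as examining the effect on signs and symptoms of MGD relative to LipiFlow. OSDI is the only patient-reported symptom measure among the effectiveness endpoints. If the plan is followed literally, its 12-week result is two separate within-arm changes.

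Those changes cannot say whether one device does better than the other. They also mix any treatment effect with regression to the mean, because entry is selected on the same scale ("Ocular Surface Disease Index (OSDI) score between 23-79"). That component is expected to be equal in the two arms under randomisation, so a between-arm contrast removes it and a within-arm test does not. A week-12 comparison added after the data are seen would be post hoc.

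Separately, the week-4 test uses raw change scores. It does not correct for chance imbalance in baseline OSDI, and it generally gives a wider interval than an analysis adjusted for baseline, which the plan already uses for TBUT and MGS.

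**Working it through.** **1. What is specified, endpoint by endpoint**

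| Endpoint | Between-arm analysis, week 4 | Between-arm analysis, week 12 | Baseline covariate |
|---|---|---|---|
| TBUT | Yes (3.4.1) | Yes (3.4.2, item 3) | Yes |
| MGS | Yes (3.4.2, item 2) | Yes (3.4.2, item 2) | Yes |
| OSDI | Yes (3.4.2, item 1) | None stated | No |

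**2. Does other text fill the empty cell?**

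- The 12-week sentence names no endpoint. It is the only text under the TBUT item, so without it TBUT at 12 weeks would have no analysis. The MGS item names 12 weeks itself, which would be redundant under a general rule. Section 3.4.3 presupposes a 12-week non-inferiority test for TBUT, which this sentence supplies.
- Section 3.4.3 concerns TBUT only.
- Section 3.1 says "Statistical comparisons within each group will be performed using appropriate statistical methods or models", which is again within arms. It then defers unspecified matters: "Further details will be described in the statistical analysis plan, which will be finalized prior to the study database lock". That names no week-12 OSDI comparison.

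**3. What the within-arm tests can show**

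The plan gives no OSDI figure to reproduce. Take the 44 evaluable patients per arm from section 3.7 and work in units of the SD of the change score.

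- A paired t-test in one arm is significant at the two-sided 5% level when the mean change exceeds t(0.975, 43)/√44 = 2.017/6.633 = 0.30 SD. Both arms can pass that threshold whatever the gap between them.
- The unadjusted between-arm difference has a 95% CI half-width of t(0.975, 86) × √(2/44) = 1.988 × 0.213 = 0.42 SD. This is the estimate that the plan does not call for at week 12.

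**4. Value of the baseline covariate**

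Let ρ be the correlation of baseline with follow-up OSDI, k the ratio of baseline SD to follow-up SD, and σ the follow-up SD. The documents give neither ρ nor k, so both are assumed.

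- Variance of change: σ²[(1 − ρ²) + (k − ρ)²]
- Residual variance after adjusting for baseline: σ²(1 − ρ²)
- Ratio R = (1 − ρ²) / [(1 − ρ²) + (k − ρ)²]

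Example with ρ = 0.5 and k = 1: 0.75 / (0.75 + 0.25) = 0.750. The last column is 44/R, the size per arm at which an unadjusted analysis would be equally precise.

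| k | ρ | R | Fall in variance | 44/R |
|---|---|---|---|---|
| 0.8 | 0.3 | 0.785 | 22% | 56.1 |
| 0.8 | 0.5 | 0.893 | 11% | 49.3 |
| 0.8 | 0.7 | 0.981 | 2% | 44.9 |
| 1 | 0.3 | 0.650 | 35% | 67.7 |
| 1 | 0.5 | 0.750 | 25% | 58.7 |
| 1 | 0.7 | 0.850 | 15% | 51.8 |
| 1.25 | 0.3 | 0.502 | 50% | 87.6 |
| 1.25 | 0.5 | 0.571 | 43% | 77.0 |
| 1.25 | 0.7 | 0.628 | 37% | 70.1 |

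R ignores the cost of estimating the slope. With 88 patients that cost multiplies R by about 1 + 1/(88 − 4) = 1.012, which takes roughly one percentage point off each fall (the 2% becomes about 1%). When k = ρ there is no gain.

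Entry restricts baseline OSDI to 23–79 while follow-up is unrestricted, so k below 1 is plausible and the k = 0.8 rows deserve the most weight.

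**The case against.** The strongest reply is that the 12-week sentence takes the visit as its subject and names no endpoint, so it could be read as covering OSDI too. Its position and the three facts in step 2 above argue against that reading. At best the text is ambiguous, and that also needs correcting.

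Second, section 3.1 promises a later analysis plan that might add the comparison. That cannot be ruled out, but the supplied text does not contain it.

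Third, if the 12-week change is reported by arm with its interval, a reader can derive the unadjusted difference, since OSDI gives one score per patient and the arms are independent. This is correct: what is missing is prespecification, not data.

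Fourth, the study is open-label, OSDI is self-assessed, and no OSDI margin is set. A between-arm test could therefore reflect expectation, and a non-significant result would not show similarity. This stands as a limit on interpretation at both visits and favours reporting an estimate with its interval.

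Fifth, the covariate is a matter of efficiency, and its size rests wholly on assumed values. This also stands, and the point is given correspondingly less weight.

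**Conclusion.** The concern holds. No between-arm OSDI analysis is specified at week 12 (0 of 1, against 1 of 1 at week 4), although the endpoint is listed for both visits. This follows from the text alone and is held with high confidence.

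The absence of baseline OSDI from the week-4 test is equally clear in the text. Its consequence is a loss of precision, not bias. The size is uncertain: a 2% to 22% variance reduction forgone at k = 0.8, and up to 50% at k = 1.25, for assumed ρ from 0.3 to 0.7.

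OSDI is secondary and carries no margin or success criterion, so the primary TBUT non-inferiority conclusion does not depend on this. The plan should be corrected, but the trial's main claim is not at risk.

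**What to change.** Replace the second OSDI bullet in section 3.4.2 with wording such as:

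> OSDI change from baseline at 4 weeks and at 12 weeks will each be analysed with a linear model (one record per patient) with treatment as fixed effect and baseline OSDI as covariate. The adjusted Tixel minus LipiFlow difference will be reported with its 95% CI. The Wilcoxon-Mann-Whitney test on change at each visit will be a sensitivity analysis.

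Also name the endpoint or endpoints to which the 12-week sentence under item 3 applies.

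This also settles the choice between the t-test and the rank test, which the plan now leaves to what is appropriate. Adding 12 weeks to the existing bullet would close the main gap on its own, but would leave the precision point and the open choice of test.

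The cost is wording only. OSDI is already collected at baseline, 4 weeks and 12 weeks, and the covariate uses one degree of freedom. No visit, patient or stated sample size changes. It should be settled before database lock, the deadline section 3.1 sets for the analysis plan.
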